#### **Safety outcomes**

Serious adverse events ('SAEs') were collected up to day 28 after inclusion. When a patient was excluded or transferred to another hospital, SAEs were only collected during the study period or up to the transfer, respectively. The following SAEs were collected and reported to the Ethical Board of the coordinating center: death, IHCA, start of renal replacement therapy, start of mechanical circulatory support, mechanical ventilation in prone position, new myocardial infarction, new serious liver failure, new cerebrovascular accident or other SAE (unexpected event resulting in a chronic and significant burden to the patient).

The number of SAEs and SUSARs will be reported for the three intervention groups separately.

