## 'Full analysis set' (ITT)

- All patients who met the in- and exclusion criteria, for whom an early administration
  of the first dose (<5 hours after ROSC) was still feasible, were randomized and treated
  according to the protocol.

  - o Including treated patients, who turned out not to meet all inclusion criteria.
  - Including treated patients, who suddenly fulfilled one of the 3 upper safety exclusion criteria.
- This analysis will contain >270 patients.

As can be understood from the information above, all randomized patients who received at least one dose ('treated') will be analyzed in the ITT-analysis, despite not fulfilling the inclusion criteria or fulfilling the exclusion criteria. These patients have not been subsequently excluded. As described earlier, further study treatment was terminated, but the patients were followed up according to the protocol.

Patients for whom deferred consent was not obtained <72 hours were excluded from the study and all analyses, except patients who died before consent could be obtained (<72 hours).

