## Secondary outcomes and analyses

The secondary outcomes are summarized in a SPIRIT figure [1].

Dichotomous secondary outcomes include:

- Delirium
  - o CAM-ICU score, ICDSC-score or DOSS-score (yes or no)
- ICU-acquired weakness
  - o Medical Research Council sum score (yes: <48, no: 48-60)
- Need for renal replacement therapy (yes or no)
- At day-28 and day-180:
  - o Survival (yes or no)

Dichotomous variables will be presented as numbers with percentages. For dichotomous variables logistic regression analyses will be carried out. Results will be presented with odds ratios and 95% confidence intervals.

Ordinal secondary outcomes include:

- Renal
  - o Calcium oxalate crystals in urine (negative, few or many)
- At day-28 and day-180:
  - o Functional outcome (mRS scale 0-6)
  - o Neurological outcome (CPC scale 0-5)

Ordinal variables will be presented as numbers with percentages. For ordinal variables a multinomial logistic regression analysis will be carried out. Results will be presented with odds ratios and 95% confidence intervals.

Continuous secondary outcomes include:

- Organ failure:
  - o SOFA-score
- Neurological:
  - o Glasgow Coma Scale
  - Neuron-specific enolase (NSE) ng/mL
  - o The Health Utilities Index-3
- Cardiac/hemodynamics:
  - $\circ$  Troponin ng/L
  - $\circ$  CK U/L
  - $\circ$  CK-MB  $\mu$ g/L
  - Vasopressor duration hours
  - Vasopressor-free days
- Lung:
  - Lung injury score
  - Ventilation duration days
  - Ventilator-free days
- Renal
  - Creatinine clearance μmol/L
  - Oxalic acid (urine) mmol/24h

- Inflammation
  - C-reactive protein mg/L
- Oxidative stress
  - Oxidation-reduction potential (ORP) mV
  - o Antioxidant capacity (AOC)  $\mu$ C
- Pharmacokinetics
  - O Plasma vitamin C concentration μmol/L
- Other clinical outcomes
  - o ICU-stay days
  - Hospital stay days

Continuous variables will be presented as mean with standard deviation or as median with interquartile range when appropriate. Q-Q plots will be assessed visually to check if a given variable follows a normal distribution. For continuous variables linear regression analyses or linear mixed model analyses will be carried out when appropriate. Results will be presented with effect sizes estimates and 95% confidence intervals. When the residuals are not normality distributed the outcome will be transformed before analysis. Analyses will be adjusted for baseline values if applicable.

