## Missing data

No missing data is expected for the primary outcome. Missing covariates used for the adjusted analysis will be imputed.

For the secondary outcomes daily and follow-up data is missing from the moment included patients are transferred to an ICU or ward of another hospital. However, questionnaires were still carried out at day 28 and 180, thereby limiting missing data on the outcome mortality. In case patients or their relative could not be reached by phone, follow up data at day 28 and day 180 was missing. Some secondary endpoints are not routinely performed in every ICU, such as the MRC-sum score, CK-MB or NSE.

The number of participants with missing data for baseline variables and other variables used in the analyses will be reported in the manuscript.

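### SAE collection stops at transfer and only counts per group are planned, so observation time is hidden and SAE deaths may fall short of day-28 deaths

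*SAP*

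**What the plan says.** All of the following is in the SAP.

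- **Window.** Under Safety outcomes, SAEs "were collected up to day 28 after inclusion". The next sentence shortens this: "When a patient was excluded or transferred to another hospital, SAEs were only collected during the study period or up to the transfer, respectively".
- **Events.** The list begins "death, IHCA, start of renal replacement therapy, start of mechanical circulatory support", so death is itself an SAE.
- **Summary.** "The number of SAEs and SUSARs will be reported for the three intervention groups separately". The section plans no number of patients with an event, observed time, rate or note on truncated collection.
- **Day-28 death as an outcome.** Secondary outcomes and analyses lists survival at day 28 and day 180 as a dichotomous outcome analysed by logistic regression. Missing data says of transferred patients that "questionnaires were still carried out at day 28 and 180, thereby limiting missing data on the outcome mortality".
- **Transfer.** Follow-up names transfer to another hospital as one of two main reasons for loss to follow-up. It promises the amount and timing of losses, but not by arm and not linked to the SAE table. Primary outcome and analyses and Planned sensitivity analyses both allow for ICU-to-ICU transfer within the first 96 hours.

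**The concern.** A count is interpretable only if the reader knows over how many patients and how much time it was collected. Here a patient transferred on day 5 without an event and one observed for 28 days without an event add the same zero. Events after transfer are lost in every arm, so the table understates absolute harm by an unstated amount. Transfer also happens after randomisation and may depend on how the patient is doing. If it differed between arms, equal risk would give unequal counts.

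The second problem concerns deaths. A death between transfer and day 28 enters the survival outcome but not the SAE record. One paper could then carry two totals for death by day 28, the lower one in the safety table, with no rule to reconcile them. Mortality is also the event on which the Interim analysis section bases the advice to stop, so the safety table should carry the complete count.

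**Working it through.** The SAP gives no figure for SAEs, transfers or deaths after transfer, so there is nothing to reproduce. The calculations below only illustrate size.

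**Inputs from the SAP:** 90 patients per arm and 270 in total (Modified intention-to-treat analysis); a 28-day window that ends at transfer (Safety outcomes).

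**Assumed inputs:** fraction transferred *f*, day of transfer *t*, risk of death between transfer and day 28 *q*, and the shape of the SAE hazard. Observation time lost to death is ignored.

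**Step 1. Time observed.** Patient-days per arm = 90 × [(1 − f) × 28 + f × t]. Full observation would be 90 × 28 = 2520.

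- f = 0.10, t = 10: 90 × (25.2 + 1.0) = 2358, or 93.6% of 2520
- f = 0.20, t = 10: 90 × (22.4 + 2.0) = 2196, or 87.1%
- f = 0.20, t = 7: 90 × (22.4 + 1.4) = 2142, or 85.0%
- f = 0.20, t = 5: 90 × (22.4 + 1.0) = 2106, or 83.6%
- f = 0.40, t = 5: 90 × (16.8 + 2.0) = 1692, or 67.1%

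A patient transferred before 96 hours loses at least 24 of 28 days (24/28 = 86%).

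**Step 2. Counts at the same true risk, constant hazard.** The ratio of expected counts equals the ratio of patient-days.

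| Arm A | Arm B | Ratio B/A |
|---|---|---|
| 10% on day 10 | 10% on day 10 | 1.00 |
| 20% on day 10 | 20% on day 5 | 2106/2196 = 0.96 |
| 10% on day 10 | 20% on day 7 | 2142/2358 = 0.91 |
| 20% on day 10 | 40% on day 5 | 1692/2196 = 0.77 |
| 10% on day 10 | 40% on day 5 | 1692/2358 = 0.72 |

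**Step 3. Deaths absent from the SAE table.** Expected number = 270 × f × q. Chance of at least one = 1 − (1 − f × q)^270.

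- f = 0.05, q = 0.05: 0.7 deaths, 49%
- f = 0.10, q = 0.10: 2.7 deaths, 93%
- f = 0.20, q = 0.20: 10.8 deaths, almost 100%

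**Step 4. Does a rate per patient-day repair the count?** Take transfer on day 7, with 45% transferred in one arm and 20% in the other, and equal true risk. The share of time observed is 1 − 0.75f, because (28 − 7)/28 = 0.75. That is 0.6625 and 0.85.

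- *Constant hazard:* the count ratio is 0.6625/0.85 = 0.78. The rate ratio is 1.00, so the rate removes the distortion.
- *80% of events in days 0 to 7 (assumed), the rest spread evenly:* the share of events observed is 1 − 0.20f, or 0.91 and 0.96. The count ratio is 0.91/0.96 = 0.95. The rate ratio is (0.91/0.6625)/(0.96/0.85) = 1.374/1.129 = 1.22.

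With early events the count is off by about 5%, while the crude rate makes the sooner-transferred arm look 22% worse. A crude rate is therefore not a safe replacement for the count.

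**The case against.** The SAP plans to report SAE numbers, not to compare or test them. The trial is double-blind and randomised 1:1:1, stratified by site, and nothing in the SAP suggests that transfer differs by arm. Several listed events, such as mechanical circulatory support and prone ventilation, are plausibly early ICU events, so few may fall after transfer. Death has its own analysis at day 28 and day 180, with status sought after transfer, so truncated SAE collection does not bias the mortality result. The SAP also says openly that data are missing after transfer and promises the amount and timing of losses.

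All of this limits the size and direction of the problem. It does not supply the missing denominator or reconcile the two death counts.

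Three stronger readings are tempting and should not be drawn.

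- *The arm transferred sooner will look safer.* This needs a difference in transfer between arms, which is not documented. With equal transfer all arms are under-counted alike.
- *The death counts will disagree.* This needs at least one death between transfer and day 28, which is likely over much of the assumed range but not certain.
- *The rule for excluded patients contradicts the Full analysis set.* A reader might take excluded patients to include those whose treatment was stopped for a safety criterion, since that section says "further study treatment was terminated, but the patients were followed up according to the protocol". But the same section says that these patients were not subsequently excluded, and it reserves exclusion for patients without timely deferred consent. There is no contradiction on that reading.

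**Conclusion.** The point holds as a defect in safety reporting. SAE observation varies between patients and is not shown, every arm is under-counted after transfer, and the SAE death count may fall below the day-28 death count. No figure in the SAP is wrong, and the day-28 survival analysis is unaffected.

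The size is unknown. On the assumed ranges, between 0.7 and 10.8 of 270 patients would be deaths known at day 28 but absent from the SAE table. Distortion between arms runs from none to a deficit of about 28% under a constant hazard, and is smaller if events are early. The death mismatch follows directly from the two collection rules once one such death occurs; the distortion between arms is conditional on unequal transfer.

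**What to change.** Amend the Safety outcomes section as follows.

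1. **Death.** Take all-cause death to day 28 in the safety table from the source used for day-28 survival, including deaths after transfer. Give the number with unknown status in each arm.
2. **Denominators.** Beside the SAE counts, report by arm the patients with at least one SAE, the number transferred before day 28 and the total SAE days observed. State in the table that SAE collection ended at transfer.
3. **Time adjustment, if wanted.** Show it beside the counts, preferably as time to first SAE censored at transfer. Death is on the SAE list, so a death before transfer counts as an event. If a rate per patient-day is shown, state that it assumes a constant hazard and can mislead when events are early.

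The cost is SAP wording and a few table rows. The SAP already promises the timing of losses and seeks vital status at day 28, so items 1 and 2 should need no new collection. Small downside: censoring at transfer may be informative, because transfer can depend on the patient's condition, and this should be stated.

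Two wider changes are not proposed. SAE collection cannot be extended by an SAP dated March 2025, since the last 180-day follow-up was in August 2024. A competing-risk analysis of renal replacement therapy would redesign a secondary outcome and is not needed to repair this section.

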#### Statistical software

The statistical analysis will be carried out in SPSS version 28 and RStudio.

VITaCCA statistical analysis plan (v1.0, March 5, 2025)

